4.3 Secondary Endpoints

Effectiveness

1. Stricture Resolution

Stricture resolution will be assessed at the time of stent removal or observation of complete or partial stent migration.

Stricture resolution is defined as maintained pain relief without need for restenting or, if pain recurs, confirmation of stent patency adequate for providing drainage of the pancreatic duct.

Restenting with a non-study stent will take place if there is no improvement of clinical status (see definition in secondary endpoint 2 below) and associated persistence of the

August 28, 2017

Boston Scientific
WallFlex Pancreatic Pivotal Protocol
91067616 Rev/Ver AK
Page 20 of 64

stricture based on imaging. Imaging will be conducted per standard of practice and may be prompted by lack of improved clinical status and may consist of non-invasive imaging or pancreatogram. A pancreatogram will only be performed if an ERCP is necessitated for a reintervention with or without restenting.

NOTE: Patients who are restented for recurring pain (VAS Pain Score of ≥ 20) will be considered a failure for stricture resolution and the primary endpoint and may only be restented with a non-study stent.

Restenting with a new study stent may only occur during the initial stent placement procedure for such situations as stent misplacement, improper stent size choice, or other conditions, as necessary and will not be considered a secondary effectiveness stricture resolution endpoint failure or a primary effectiveness endpoint failure.

2. Improved clinical status compared to baseline assessed at each study visit.

Improved clinical status is defined as improvement in at least one and deterioration in none of the following: Pain, Weight and Quality of Life (QOL)

- *Pain: Scored between 0 and 100 as the mean of the VAS Pain Score and Frequency of Pain sectors of the Izbicki pain scale.*
- *Weight is measured*
- *Quality of life: Recorded using SF12*

3. Recurrence of Stricture documented by recurrence of pain with loss of adequate pancreatic duct drainage.

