Recurrence of stricture is defined as need for restenting. Restenting will take place if there is deterioration of clinical status (see definition in secondary endpoint 2 above) and documented recurrent stricture based on imaging. Imaging may be prompted by deterioration of clinical status and may consist of non-invasive imaging or of a pancreatogram. A pancreatogram will only be performed if an ERCP is necessitated for a reintervention with or without restenting.

4. Stent Functionality

Stent functionality will be assessed from stent placement until stent removal or observation of complete or partial stent migration.

Stent functionality is defined as adequate pancreatic duct drainage reflected by reduction of pain and lack of restenting.

5. Izbicki pain scale assesed at each study visit

The Izbicki pain scale (see appendix in section 22.1) has four sectors related to severity of pain, frequency of pain, analgesic medication, and disease-related inability to work.

6. Average daily narcotic dose for prior month assessed at each study visit

7. Maintenance of the VAS Pain Score and Frequency of Pain Score recorded at 6 months post-stent removal compared with that recorded at the time of plastic stent removal, for patients with plastic pancreatic stent indwelling immediately prior to study stent placement

August 28, 2017

Boston Scientific
WallFlex Pancreatic Pivotal Protocol
91067616 Rev/Ver AK
Page 21 of 64

Technical Success

8. Ability to deploy the stent in satisfactory position (Stent Placement Success).

Satisfactory position is defined as the stent being across the stricture, without visible occluding impaction at the genu of the pancreatic duct and with distal end of the stent visible in the duodenum. Ease of placement will also be assessed.on a 5 point Likert scale.

9. Successful endoscopic stent removal (Endoscopic Stent Removal Success).

Endoscopic stent removal success is defined as ability to remove stent endoscopically (forceps, snare) without serious stent removal-related adverse events. Ease of removal will also be assessed.on a 5 point Likert scale. Use of stent-in-stent removal technique will be considered a removal failure. If stent migration is noted at time of study stent removal, the patient will be excluded from this endpoint's analysis.

Safety and Device Events

10. Device Events, including findings not associated with adverse events, such as but not limited to asymptomatic stent migration.

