7.4 Scoring System

7.4.1 Izbicki Scoring System

The Izbicki Pain Scale incorporates four elements: 1) patient self-estimation of intensity of pain using a visual analog scale (VAS), 2) the frequency of pain attacks, 3) analgesic medication usage and 4) the time periods of inability to work. The sum of the rank values divided by four gives the final value of the pain score. See Appendix 22.1 for the Pain Scale.

Patients will be asked to report on the average pain experienced since the prior visit when reporting pain via VAS for the first element of the Izbicki Pain Scale. Patients will be asked to report the average frequency of pain attacks experienced since the prior visit for the second element of the Izbicki Pain Scale. Please see Appendix 22.5 for further guidance on collecting the VAS and frequency of pain attacks information.

Note: For centers with medication types that do not align with section 3 of the Izbicki Pain scale, relevant corresponding medication types may be made available for scoring.

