8.2.2 Post Procedure Data

Post-procedure information will be collected at regularly scheduled follow-up examinations as detailed in the clinical study event schedule and will be summarized using descriptive statistics for continuous variables (e.g., mean, standard deviation, n, minimum, maximum) and frequency tables or proportions for discrete variables.

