22.5 Guidance on Collecting VAS Pain Score and Frequency of Pain Attacks Information

The Izbicki Pain Scale incorporates the following four elements in its measurement of pain:

- 1) patient self-estimation of intensity of pain using a visual analog scale (VAS)
- 2) the frequency of pain attacks
- 3) analgesic medication usage
- 4) the time of disease-related inability to work

The sum of the rank values divided by four gives the final value of the pain score. Please see Appendix 22.1 for more information. The Izbicki Pain Scale will be collected at every study visit. The information below will serve as guidance when collecting information for the first two elements of the Izbicki Pain Scale.

When reporting pain via VAS for the first element of the Izbicki Pain Scale, patients will be asked to report on the average pain experienced since the prior study visit. For the second element of the Izbicki Pain Scale, patients will be asked to report the average frequency of pain attacks experienced since the prior study visit. The manner in which these two questions are posed will depend upon the patient's pain pattern.

What is the patient's pain pattern?

Short and relapsing episodes of pain separated by periods of pain remission	Prolonged periods of fairly constant pain	Unknown or indistinguishable pattern of pain

1st Study Visit Within the previous three months, how strong was your most severe bout of pain? & Within the previous three months, how frequently did you experience a bout of pain?
 
Follow-up Study Visit Since the last study visit, how strong was your most severe bout of pain? & Since the last study visit, how frequently did you experience a bout of pain?
	
1st Study Visit Within the previous three months, how would you score the average level of pain you experienced? & Within the previous three months, how frequently have prolonged periods of pain occurred?
 
Follow-up Study Visit Since the last study visit, how would you score the average level of pain you experienced? & Since the last study visit, how frequently did prolonged periods of pain occur?
	
1st Study Visit Within the previous three months, how would you score your pain? & Within the previous three months, how frequently have you experienced pain?
 
Follow-up Study Visit Since the last study visit, how would you score your pain? & Since the last study visit, how frequently have you experienced pain?

August 28, 2017

Boston Scientific

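### For patients asked about their worst bout of pain, the VAS looks back three months at baseline but about 30 days at Month 1 and 60 days at Month 3, which biases early change from baseline towards improvement in secondary endpoints 2 and 5

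*Combined protocol and SAP*

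**What the plan says.** Appendix 22.5 words the pain questions by pain pattern. The relapsing-pattern form asks at the first visit: "Within the previous three months, how strong was your most severe bout of pain". At later visits it asks: "Since the last study visit, how strong was your most severe bout of pain". The constant-pain form asks at follow-up: "Since the last study visit, how would you score the average level of pain you experienced". The form for an unclear pattern asks: "Since the last study visit, how would you score your pain". All three use three months at the first visit and the time since the last visit afterwards.

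Section 7.4.1 gives one instruction for everyone: "Patients will be asked to report on the average pain experienced since the prior visit when reporting pain via VAS". The introduction to Appendix 22.5 says the same. Neither fits the worst-bout form.

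Two secondary endpoints in Section 4.3 use these scores visit by visit. Endpoint 2 is "Improved clinical status compared to baseline assessed at each study visit". It requires improvement in at least one of pain, weight and quality of life, with none deteriorating, and sets no size of change. Its pain score is the mean of the VAS and frequency sectors. Endpoint 5 is the full scale at each visit: "The Izbicki pain scale (see appendix in section 22.1) has four sectors related to severity of pain, frequency of pain, analgesic medication", plus inability to work.

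Section 8.2.2 says: "Post-procedure information will be collected at regularly scheduled follow-up examinations as detailed in the clinical study event schedule", with descriptive summaries. No section adjusts for the length of the look-back.

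**The concern.** The worst-bout VAS is a maximum over the look-back period. With bouts of varying severity, a longer period gives a higher expected maximum even if the disease is the same. Comparing a 30-day maximum with a three-month maximum therefore favours an apparent fall.

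Two readings are at stake. In endpoint 2 any fall in pain can count as improvement, and the same artefact can hide a true deterioration. In endpoint 5 the by-visit summaries can suggest an early gain after placement that fades by Month 6, although only the length of the period has changed.

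**Working it through.** **Look-back periods.** These are differences between the visit days in Sections 7.1 and 7.7 to 7.10. Pain is also scored at the placement visit (Section 7.6.2), so the Month 1 question reaches back to placement. Baseline is taken as 90 days.

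**Chance of a lower score with no true change.** Suppose bouts are exchangeable over time, severity is continuous and the two periods do not overlap. The worst bout of both periods together is then equally likely to fall on any day. With a follow-up period of w days,

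P(follow-up VAS < baseline VAS) = 90 / (90 + w).

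This needs no bout rate or VAS distribution.

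| Visit | w in days (allowed range) | Formula | Probability (range) |
|---|---|---|---|
| Month 1 | 30 (25-35) | 90/120 | 75% (72-78%) |
| Month 3 | 60 (45-75) | 90/150 | 60% (55-67%) |
| Month 6, removal | 90 (65-115) | 90/180 | 50% (44-58%) |
| Post-removal Month 3 | 90 (75-105) | 90/180 | 50% (46-55%) |
| Post-removal Month 6 | 90 (60-120) | 90/180 | 50% (43-60%) |

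**Size in VAS points.** This needs assumptions that the documents do not supply: Poisson bouts at 1, 2 or 3 a week, and bout VAS normal with mean 50 and SD 10, 15 or 20, clipped to 0-100. Simulation used 40,000 patients per setting. At one bout a week and SD 20:

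| Period | Mean worst-bout VAS | Shift from 90 days | Two-sector score (shift/2) | Four-sector score (shift/4) |
|---|---|---|---|---|
| 30 days | 68.4 | -13.8 | -6.9 | -3.5 |
| 60 days | 77.9 | -4.3 | -2.2 | -1.1 |
| 90 days | 82.2 | 0 | 0 | 0 |

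The last two columns hold the other sectors fixed. Over all nine settings the VAS shift runs from -5.0 to -13.8 at Month 1 and from -1.7 to -4.3 at Month 3, so the table shows the largest case. The simulated chance of a lower score was 74-76% at Month 1, 58-60% at Month 3 and 48-50% at Month 6. It was lowest where clipping at 100 produced ties.

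**Average-level question.** In the same simulation the chance of a lower score was about 50% at every visit. The shift was at most -0.7, from the 1.4% of weekly-bout patients with no bout in 30 days, who were scored 0 (0.014 × 50 = 0.7).

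**Check of the remedy.** The maximum of all scores from placement to Month 3 covers 30 + 60 = 90 days, and 90/(90 + 90) = 50%.

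**The case against.** The strongest reply is that only one of three question forms asks for a maximum. The average-level form has no expected shift, the unclear-pattern form names no maximum, and the general instruction asks everyone for an average. A reader might infer from the differing look-backs that all early pain results improve by construction. The documents do not support that. They give no pattern mix, and stent-expansion pain, which Section 4.2 anticipates, can raise Month 1 scores. The net error at Month 1 across the trial therefore has no known size or sign.

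A reader might also infer that many unchanged patients would appear to have their pain halved. That holds only for sparse bouts. Inclusion criterion 7 asks for pain weekly or more often. At about 4.3 bouts a month (VAS mean 50, SD 20), the VAS halves by chance in about 6% at Month 1 and 0.4% at Month 3. The two-sector score does so in under 2% and about 0.02%. Endpoint 2 has no halving rule in any case. For the same reason the frequency item moves little in patients with no true change.

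A third tempting reading is that the primary effectiveness result is contaminated. On schedule it compares about 90 days with three months. Mismatch can arise only in particular cases: after unscheduled visits, which also score pain and shorten the next look-back, or when a Month 1 or Month 3 score is carried forward for missing 6-month data (Section 8.1.2). It can also arise where baseline is the plastic-to-study stent exchange, since that score may look back less than three months. The 90-day baseline used above does not hold for those patients.

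Finally, endpoints 2 and 5 have no stated hypothesis test, and pain is one of three components of endpoint 2. This limits the consequence. It does not remove the bias in patients asked the worst-bout question, because no minimum change is set.

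**Conclusion.** The concern holds for patients asked the worst-bout question, at Month 1 and Month 3, in the pain component of endpoint 2 and the by-visit summaries of endpoint 5. The 75%, 60% and 50% figures rest on stable disease, a three-month baseline look-back and visits on schedule. The point shifts of about -14 and -4 on the VAS also rest on assumed weekly bouts with mean 50 and SD 20. The two-sector score moves by half as much and the four-sector score by a quarter. The trial-level effect cannot be computed. This is a matter of interpreting secondary endpoints and does not call the primary analysis into question.

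**What to change.** In the SAP:

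- Base the pain component of endpoint 2, and any change from baseline for endpoint 5, on visits whose look-back matches the baseline look-back. State the actual look-back where baseline is the stent-exchange score.
- Report Month 1 pain descriptively with its 30-day period stated, and leave it out of the improved/not improved classification.
- At Month 3, for worst-bout patients, use the maximum VAS over all scores collected from placement to Month 3, including unscheduled visits. Show the as-collected Month 3 score beside it.
- Apply the same maximum rule within later intervals that contain an unscheduled visit.
- State that the frequency item stays on its collected period, since the maximum repairs only the VAS.
- Record which question form each patient was asked, and reconcile the average-pain instruction in Section 7.4.1 and the introduction to Appendix 22.5 with the worst-bout question.

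The scores are already collected, so the analysis change is mainly wording. However, no section says that the question form is recorded, so a data field or recovery from site records may be needed. Section 4.3 defines endpoint 2 at every visit, so removing Month 1 changes that definition and should be documented as such. The price is no change-from-baseline result at Month 1, and a pooled Month 3 VAS that includes peri-procedural pain.
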